### C. Initial evaluation

Patients will be seen in the outpatient clinic of the NIH Clinical Center and undergo the following evaluation before starting therapy. Patients requiring a liver biopsy will be admitted to the Clinical Center for a percutaneous liver biopsy under ultrasound guidance.

1. History and physical examination.
2. Blood tests – complete blood count (CBC with differential and platelet count), prothrombin time, partial thromboplastin time, sedimentation rate, Chem-20 (which includes alanine aminotransferase [ALT], aspartate aminotransferase [AST], direct and total serum bilirubin, albumin, total protein, lactic dehydrogenase [LDH] creatine phosphokinase [CK], sodium, chloride, bicarbonate, potassium, blood urea nitrogen, creatinine, uric acid, calcium, and phosphorus), alpha-fetoprotein, amylase, lipase, immunoglobulin G, A and M, thyroid stimulating hormone (TSH), antinuclear antibody (ANA), rheumatoid factor, lipid panel (triglycerides, total cholesterol, high density lipoprotein associated cholesterol, low density lipoprotein associated cholesterol), hepatitis B viral markers (HBsAg, anti-HBs, HBeAg, and anti-HBe), anti-HCV, anti-HDV, and anti-HIV. An additional 10 ml. of serum will be collected and stored at –20 degrees Celsius for future research testing.
3. Baseline HBV DNA level by quantitative PCR (Amplicor™: Roche, lower limit of detection 20 IU/ml) and HBV genotyping (HBV Genotyping Line Probe Assay, Innogenetics, Belgium).
4. Routine urinalysis, random total protein/creatinine ratio, and two 24-hour urines for creatinine clearance and protein excretion.
5. Pregnancy test for women of childbearing potential.
6. Patients who have not had them within the previous year will undergo chest X-ray, electrocardiogram (EKG), and abdominal ultrasound.

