Patients will be seen in the outpatient clinic at weeks 0, 2, 4, 8, 12, 24, 36, and 48 weeks during the first year of therapy and at 12 week intervals thereafter.

At 48 weeks, all patients will be readmitted to the NIH Clinical Center and undergo a repeat thorough medical evaluation and liver biopsy. Patients in the salvage arm will be excluded from undergoing the 48 week liver biopsy. Continuation of therapy thereafter will depend upon both tolerance and benefit. All patients will undergo a 192 week follow-up biopsy to assess long-term efficacy and durability of response. Benefit is described in Section F “Assessment of Response” and tolerance in Section G “Assessment of Toxicity.”

The side effects will be monitored regularly. Tenofovir and emtricitabine will be stopped if moderate side effects attributable to either or both medications develop and persist for at least one week or on repeat testing. The medication(s) can be restarted if the adverse event resolves and does not appear to be related to either or both medications.

In the absence of toxicity attributable to either agent, combination therapy with tenofovir and emtricitabine or monotherapy with tenofovir will be continued for 192 weeks. Study medication/s will be discontinued if there is serological evidence of resolution of chronic hepatitis B, as shown by loss of HBsAg, documented on two serum samples taken at least six months apart.

Patients on therapy who develop evidence of drug resistance with elevations of serum aminotransferase levels twice above normal and HBV-DNA levels greater than  $10^6$  IU/ml will be switched to alternative therapies if mutually agreed between the patient and the investigators.

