#### **F. Assessment of response:**

In this study, the combination of tenofovir and emtricitabine and tenofovir monotherapy will be evaluated for long-term effects on chronic hepatitis B in both HBeAg-positive and -negative cohorts and in treatment naïve and those with resistance to lamivudine, adefovir, entecavir or all agents.

Definitions:

- a) **Full virological response:** absence of detectable HBV DNA by PCR ( $<10^2$  IU/ml)
- b) **Partial virological response:** suppression of HBV DNA to  $<10^4$  IU/ml but  $>10^2$  IU/ml
- c) **Serological response (HBeAg-positive patients only):** loss of detectable HBeAg.
- d) **Full biochemical response:** fall of serum ALT into the normal range ( $<41$  IU/L)
- e) **Partial histological response:** improvement in liver histology as defined by a decrease in the inflammatory component of the histological activity index (HAI) score by 3 points or more and no worsening of the Ishak fibrosis score. Histological responses will be assessed after 48 and 192 weeks of therapy.
- f) **Complete histological response:** improvement in liver histology as defined by a decrease in the inflammatory component of the histological activity index (HAI) score by 3 points or more and no worsening of the Ishak fibrosis score and a decrease of the HAI score to 3 or less. Histological responses will be assessed after 48 and 192 weeks of therapy.
- g) **Combined response:** the combination of a virological, serological, biochemical and histological response.
- h) **Complete Response:** Loss of HBsAg. A complete response is the major focus and most hoped for outcome of long-term antiviral treatment of hepatitis B. A complete response is reason for stopping all antiviral treatment.

Beneficial responses are also characterized as initial, maintained or sustained:

- a) **Initial response:** full virological or biochemical response occurring within the first 24 weeks of therapy.

- b) **Maintained response:** virological, serological, biochemical, histological, or combined response present at the time of last observation in a patient still receiving therapy.
- c) **Sustained response:** virological, serological, biochemical, histological or combined response present at the time of last observation and at least six months after stopping therapy.

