The primary study endpoints will be a maintained full virological response after 48 weeks and 192 weeks of therapy (the two points of formal statistical analysis). The major secondary endpoint will be absence of a failure of therapy and absence of resistance mutations. Other endpoints to therapy will be loss of HBeAg, loss of HBsAg, normalization of serum ALT, improvements in histology activity index, improvements in hepatic fibrosis, improvement in Fibroscan scores and decrease in HVPg. Other endpoints will be improvement in symptom scores at 48 and 192 weeks.

Failure of therapy may be due to primary non-response, lack of virological response, breakthrough, or relapse, as defined below.

A **primary non-response** is defined as lack of decrease in HBV DNA levels by at least 1  $\log_{10}$  after at least 24 weeks of therapy in the absence of non-compliance.

A **failure in virological response** is defined as failure to suppress HBV DNA below  $10^4$  IU/ml after 48 weeks of therapy in the absence of non-compliance.

A **breakthrough** is defined as a  $\geq 1 \log_{10}$  IU/L increase in HBV DNA level from nadir in two consecutive samples at least one month apart in a patient with an initial full virological response in the absence of non-compliance.

A **relapse** is defined as a rise in HBV DNA levels to above  $10^4$  IU/ml or of ALT to above the normal range after therapy is stopped in a patient who previously had a maintained full virological response.

These definitions are all interlocking but help to define response and non-response rates and whether therapy has a sustained effect.

**Stopping therapy:** Therapy will be continued indefinitely or until one of the following endpoints are reached:

1. **Failure of therapy:** If HBV DNA levels remain consistently  $>10^4$  IU/ml after one year of continuous therapy, patients will be offered alternative therapy or the option to stop therapy. Alternative therapies may include switching to combination therapy if they were receiving monotherapy or switching to entecavir if receiving combination therapy. Patients who fail to respond may also elect to receive a course of peginterferon. These options are available at the NIH Clinical Center on an open-label basis.

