ii) **Toxicity.** Either intolerance to tenofovir or the combination of tenofovir and emtricitabine or development of worsening renal function would be a reason to stop therapy (see below **The risks and hazards of tenofovir and emtricitabine combination therapy** for management of tenofovir toxicity.)

In either situation, entecavir or peginterferon would be options for alternative therapy. Discontinuation of therapy due to toxicity will be considered failure of therapy and, if treated, not as a part of this protocol.

iii) **Clearance of HBsAg.** Patients who become and remain HBsAg and HBV DNA negative for at least six months will have therapy discontinued. These patients will be monitored at 4 week intervals for the next 6 months and then every 12 weeks. If HBsAg returns or if HBV DNA levels rise above  $10^4$  IU/ml, therapy will be reinstated. Patients who clear HBsAg who are anti-HBs negative will be given a course of HBV vaccine (0, 1 and 4-6 months).

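### Section D stops study drug on HBsAg loss alone, Section F item iii) also requires negative HBV DNA, and nothing says which rule governs

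*Combined protocol and SAP*

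**What the plan says.** Five places in the combined protocol and SAP deal with stopping treatment after loss of HBsAg.

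- **Section D (Treatment).** Study drug is to be discontinued on serological evidence of resolution, "as shown by loss of HBsAg, documented on two serum samples taken at least six months apart". HBV DNA is not mentioned.
- **Section F (Assessment of response), Stopping therapy.** The list opens with "Therapy will be continued indefinitely or until one of the following endpoints are reached". Item iii), on clearance of HBsAg, reads "Patients who become and remain HBsAg and HBV DNA negative for at least six months will have therapy discontinued".
- **Section F, definition h).** Complete response is HBsAg loss, and "A complete response is reason for stopping all antiviral treatment". There is no HBV DNA condition.
- **Hypotheses and Issues, question 4 for treatment-naïve patients.** Patients who lose HBsAg are withdrawn from six months after the loss, again with no HBV DNA condition. They are then watched for returning viral activity or raised ALT.
- **Opening of the Protocol section.** Patients who have lost HBsAg have a monitored withdrawal. Neither a duration nor HBV DNA is mentioned.

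**The concern.** Section D and Section F item iii) are both written as mandatory, and they can give opposite instructions for the same patient. The one who matters most is HBsAg negative and still HBV DNA positive: a clinician following Section D withdraws treatment from a viraemic patient, while one following Section F continues it.

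The protocol treats withdrawal as hazardous. The Background reports decompensation or death after stopping therapy, especially in advanced disease. It also reports flares in 23% of patients after emtricitabine was withdrawn, with one liver transplantation. These figures are not specific to patients who have lost HBsAg, so they show the kind of harm and not its rate here.

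The conflict also affects question 4, which asks whether therapy can be stopped safely after HBsAg loss. The answer depends on which patients were stopped, and the two rules can select different groups.

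**Working it through.** **The plan's own figure.** Section I states 86% power for Fisher's exact test, two-sided 0.05, 0.94 against 0.70, with 50 per group. Exact enumeration over Binomial(50, 0.94) and Binomial(50, 0.70) gives 85.7%, so it reproduces. The calculation takes no input from either stopping rule. The rest is a comparison of text.

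**Step 1: apply each rule to the same patient.** The period is the same in both rules, at least six months. Section D needs two negative HBsAg samples that far apart. Section F item iii) needs both markers to become and to remain negative.

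| Course over at least six months | Section D | Section F iii) |
|---|---|---|
| HBsAg negative throughout, HBV DNA negative throughout | Stop | Stop |
| HBsAg negative throughout, HBV DNA positive | Stop | Continue |
| HBsAg negative, then positive, then negative; first and last samples at least six months apart | Stop, read literally | Continue |

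The second row comes from the HBV DNA condition. The third comes from the difference between two samples and continuous negativity. It can arise in practice because Section E tests HBsAg every 12 weeks, so at least one scheduled test falls between two samples six months apart.

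**Step 2: look for a statement of precedence.** Section D does refer to Section F, but only for what counts as benefit when continuation after week 48 is decided. The HBsAg sentence comes later in Section D and carries its own complete test. Section F does not mention the Section D rule. Question 4, the Protocol opening and definition h) name HBsAg loss alone and refer to neither rule. Nothing ranks the two.

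**Step 3: what negative HBV DNA means in item iii).** The item gives no number. Definition a) in Section F equates "absence of detectable HBV DNA by PCR" with a level below 10² IU/ml. Section C, item 3, gives the assay a "lower limit of detection 20 IU/ml". A result from 20 up to 10² IU/ml is therefore detectable by the assay but negative under definition a). Item iii) needs the number to be usable as the single rule.

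**Step 4: reach into the primary endpoint.** The primary endpoint is a maintained full virological response after 48 and 192 weeks. Section F defines a maintained response as one present at last observation in a patient still receiving therapy. Suppose a patient is HBsAg negative and HBV DNA positive at some visit before week 192. Under Section D drug stops, so that patient is no longer on therapy. Under Section F drug continues, and HBV DNA could be suppressed by week 192. The choice of rule can therefore change that patient's classification, but only for this uncommon combination of markers.

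**Step 5: feasibility.** Section E already measures HBV DNA at every visit and HBsAg every 12 weeks during therapy. Either rule can be applied with scheduled samples.

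**The case against.** The best defence is that Section F item iii) is simply the detailed version of Section D. Section D stops drug for resolution of hepatitis B and offers HBsAg loss as the evidence, so withdrawal from a viraemic patient is a strained reading. Section F has a dedicated stopping list, and question 4 presumes suppressed HBV DNA because it watches for its return. This supports item iii) as the probable intent. It does not remove the conflict: Section D says how resolution is shown, and HBV DNA is not part of it.

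One can also argue the reverse. Section D, question 4, the Protocol opening and definition h) all cite HBsAg loss alone, and only item iii) adds HBV DNA, so preferring item iii) is a judgement. That stands. The reasons for preferring it are its place in the stopping list and that it errs towards continuing treatment in a viraemic patient.

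A reader might also infer that Section D creates a gap in re-treatment. Item iii) restarts therapy "If HBsAg returns or if HBV DNA levels rise above" 10⁴ IU/ml, and relapse means HBV DNA above that level or a rise of "ALT to above the normal range after therapy is stopped in a patient who previously had a maintained full virological response". A stopped patient between 10² and 10⁴ IU/ml with normal ALT meets neither trigger. But a patient correctly stopped under item iii) can later reach the same range, so the gap exists under both rules and choosing one does not close it. It is not part of this point.

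**Conclusion.** The point holds as a minor but genuine inconsistency. Section D, as written, states a rule that conflicts with the stopping list in Section F. Taken literally, it would withdraw drug from a patient who is HBsAg negative and HBV DNA positive.

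The number affected is likely very small and may be zero. The Background and question 4 both describe HBsAg loss as following long suppression of HBV DNA, which suggests that the discordant state is uncommon. A reader might be tempted to derive a count from the 5% to 10% yearly HBsAg loss expected in question 4. That also needs the share still HBV DNA positive at HBsAg loss, which the documents do not give, so any count would rest on an invented figure.

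Two other inferences go too far. One is that the HBV DNA condition is the only difference; the third row of the table shows that it is not. The other is that the primary comparison cannot be touched, on the ground that a patient at or above 10² IU/ml at an analysis visit is already a non-responder. The rule also decides who is still on therapy at week 192, and the definition of maintained response depends on that. The supportable statement is that any such effect is at most negligible. The main consequences are for the safety of withdrawal and for who counts as stopped in question 4.

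This rests on the text alone and assumes that no instruction outside the documents settles precedence.

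**What to change.** 1. In Section D, replace the sentence on stopping for HBsAg loss with a cross-reference to Section F, Stopping therapy, item iii), as the single governing rule.
2. In item iii), state that HBV DNA negative means below 10² IU/ml, as in definition a).
3. Point question 4, the withdrawal sentence in the Protocol opening, and the last sentence of definition h) to item iii). Leave complete response itself defined as HBsAg loss.

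The cost is protocol wording only. The tests are already scheduled in Section E, and no endpoint definition changes. The downside is that the few patients who are HBsAg negative but HBV DNA positive stay on drug longer, until both markers have been negative for six months.

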### **E. Monitoring**

Patients will be seen, interviewed, and have blood and urine tests taken at regular intervals according to the following schedule (Appendix A): on at least two occasions during the six months before treatment (Screen 1 and 2) including at the time of liver biopsy and initial evaluation, on day 0 (before first administration of drug) and at weeks 2, 4, 8, 12, 24, 36, and 48 after starting therapy. Thereafter, the patients will be seen every 12 weeks while on therapy. At each visit, the patients will be asked about symptoms and possible side effects and fill out a symptom and side effect questionnaire. Blood samples will be drawn for CBC and biochemical tests including chemistry-20 panel (ALT, AST, alkaline phosphatase, creatine kinase, lactic dehydrogenase, direct and total bilirubin, sodium, potassium, chloride, bicarbonate, glucose, BUN, creatinine, albumin, total protein, calcium, and phosphate), and 10 ml of research blood. HBV DNA will be measured at every clinical visit during therapy and more often if needed, such as to investigate viral breakthrough. In addition, HBsAg, HBeAg and anti-HBe will be tested every 12 weeks during therapy and anti-HBs if appropriate. An additional sample will be collected for routine storage to allow for repeat testing. Urine will be collected for urinalysis and random total protein/creatinine ratio at every visit. Twenty-four hour urine for creatinine clearance and total protein will be done at 48 weeks and 192 weeks. Women of child bearing potential will have a pregnancy test at each study visit. Women with a positive pregnancy test will be immediately withdrawn from study drug/s. Patients may be offered alternative approved therapy if clinically indicated. Immunological testing for CD4+ and CD8+ T cell responses to HBV antigens will be done before treatment for all previously untreated patients and repeated at 2, 4, 8, 12, 36 and 48 weeks for HLA-A2 positive patients. Alpha-fetoprotein levels will be measured every 24 weeks. Ultrasound or computerized tomography of the liver will be done every 24 weeks months in patients with advanced fibrosis or cirrhosis; in other patients these tests will be done at the time of 48 and 192 week liver biopsies. Fibroscan of the liver will be performed yearly. Bone mineral density will be re-assessed at 48 and 192 weeks.

At the end of the initial 48 week period of treatment, patients will be readmitted to the NIH Clinical Center and undergo the same evaluation as outlined under initial evaluation above. This evaluation will include a repeat liver biopsy. Patients in the salvage arm will be excluded from undergoing the 48 week liver biopsy. Patients who underwent hepatic venous pressure gradient measurements at the start will undergo repeat pressure measurement with concurrent transjugular liver biopsy. Patients judged to have a beneficial response to therapy will be continued on tenofovir or combination therapy and followed at 12-week intervals. If therapy is stopped (either for toxicity, resolution of hepatitis B or at the end of the trial), patients will be seen in the outpatient clinic every 4 weeks for 6 months. Thereafter, patients will be followed at 3 to 12 month intervals as is customary for the Liver Diseases Branch patients in protocol 91-DK-214 ("Evaluation of

Patients with Liver Disease”). Patients who have not had a beneficial response or a sustained response will be eligible for antiviral therapy in other protocols.

#### **F. Assessment of response:**

In this study, the combination of tenofovir and emtricitabine and tenofovir monotherapy will be evaluated for long-term effects on chronic hepatitis B in both HBeAg-positive and -negative cohorts and in treatment naïve and those with resistance to lamivudine, adefovir, entecavir or all agents.

Definitions:

- a) **Full virological response:** absence of detectable HBV DNA by PCR ( $<10^2$  IU/ml)
- b) **Partial virological response:** suppression of HBV DNA to  $<10^4$  IU/ml but  $>10^2$  IU/ml
- c) **Serological response (HBeAg-positive patients only):** loss of detectable HBeAg.
- d) **Full biochemical response:** fall of serum ALT into the normal range ( $<41$  IU/L)
- e) **Partial histological response:** improvement in liver histology as defined by a decrease in the inflammatory component of the histological activity index (HAI) score by 3 points or more and no worsening of the Ishak fibrosis score. Histological responses will be assessed after 48 and 192 weeks of therapy.
- f) **Complete histological response:** improvement in liver histology as defined by a decrease in the inflammatory component of the histological activity index (HAI) score by 3 points or more and no worsening of the Ishak fibrosis score and a decrease of the HAI score to 3 or less. Histological responses will be assessed after 48 and 192 weeks of therapy.
- g) **Combined response:** the combination of a virological, serological, biochemical and histological response.
- h) **Complete Response:** Loss of HBsAg. A complete response is the major focus and most hoped for outcome of long-term antiviral treatment of hepatitis B. A complete response is reason for stopping all antiviral treatment.

Beneficial responses are also characterized as initial, maintained or sustained:

- a) **Initial response:** full virological or biochemical response occurring within the first 24 weeks of therapy.

- b) **Maintained response:** virological, serological, biochemical, histological, or combined response present at the time of last observation in a patient still receiving therapy.
- c) **Sustained response:** virological, serological, biochemical, histological or combined response present at the time of last observation and at least six months after stopping therapy.

The primary study endpoints will be a maintained full virological response after 48 weeks and 192 weeks of therapy (the two points of formal statistical analysis). The major secondary endpoint will be absence of a failure of therapy and absence of resistance mutations. Other endpoints to therapy will be loss of HBeAg, loss of HBsAg, normalization of serum ALT, improvements in histology activity index, improvements in hepatic fibrosis, improvement in Fibroscan scores and decrease in HVPg. Other endpoints will be improvement in symptom scores at 48 and 192 weeks.

Failure of therapy may be due to primary non-response, lack of virological response, breakthrough, or relapse, as defined below.

A **primary non-response** is defined as lack of decrease in HBV DNA levels by at least 1  $\log_{10}$  after at least 24 weeks of therapy in the absence of non-compliance.

A **failure in virological response** is defined as failure to suppress HBV DNA below  $10^4$  IU/ml after 48 weeks of therapy in the absence of non-compliance.

A **breakthrough** is defined as a  $\geq 1 \log_{10}$  IU/L increase in HBV DNA level from nadir in two consecutive samples at least one month apart in a patient with an initial full virological response in the absence of non-compliance.

A **relapse** is defined as a rise in HBV DNA levels to above  $10^4$  IU/ml or of ALT to above the normal range after therapy is stopped in a patient who previously had a maintained full virological response.

These definitions are all interlocking but help to define response and non-response rates and whether therapy has a sustained effect.

**Stopping therapy:** Therapy will be continued indefinitely or until one of the following endpoints are reached:

1. **Failure of therapy:** If HBV DNA levels remain consistently  $>10^4$  IU/ml after one year of continuous therapy, patients will be offered alternative therapy or the option to stop therapy. Alternative therapies may include switching to combination therapy if they were receiving monotherapy or switching to entecavir if receiving combination therapy. Patients who fail to respond may also elect to receive a course of peginterferon. These options are available at the NIH Clinical Center on an open-label basis.

ii) **Toxicity.** Either intolerance to tenofovir or the combination of tenofovir and emtricitabine or development of worsening renal function would be a reason to stop therapy (see below **The risks and hazards of tenofovir and emtricitabine combination therapy** for management of tenofovir toxicity.)

In either situation, entecavir or peginterferon would be options for alternative therapy. Discontinuation of therapy due to toxicity will be considered failure of therapy and, if treated, not as a part of this protocol.

iii) **Clearance of HBsAg.** Patients who become and remain HBsAg and HBV DNA negative for at least six months will have therapy discontinued. These patients will be monitored at 4 week intervals for the next 6 months and then every 12 weeks. If HBsAg returns or if HBV DNA levels rise above  $10^4$  IU/ml, therapy will be reinstated. Patients who clear HBsAg who are anti-HBs negative will be given a course of HBV vaccine (0, 1 and 4-6 months).

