3. Will combination therapy yield a higher rate of beneficial response than monotherapy? To address this issue, several definitions for response will be made and compared between the two arms. The primary response definition will be absence of detectable HBV DNA by PCR-based methods ( $<10^2$  IU/ml) at 48 weeks and 192 weeks. Secondary response endpoints will be HBV DNA levels  $<10^4$  IU/ml at 48 and 192 weeks as well as both HBV DNA level definitions at 96, 144 and 240 weeks and at the time of last assessment (= maintained response). Other secondary response endpoints will be clearance of HBeAg (among HBeAg-

positive patients), loss of HBsAg, normalization of ALT, and improvement in liver biopsy histology scores using two definitions: (1) decrease of 3 points in histological activity index (HAI) compared to pre-treatment biopsy results with no worsening of fibrosis and (2) decrease of 3 points in HAI compared to pre-treatment biopsy results and to a total HAI score of 3 or less with no worsening of fibrosis. The investigators believe that long-term tenofovir and emtricitabine will provide HBV DNA suppression response rates of greater than 90%. Non-responders will likely be patients who are not compliant. Thus, this study will be designed to show superiority of combination therapy to monotherapy, and the investigators believe that this study will set the standard of care for chronic hepatitis B.

4. Will long term maintenance of HBV DNA suppression result in loss of HBsAg and the ability to safely stop therapy? To address this issue, patients will be tested for HBsAg at six monthly intervals. Patients who become HBsAg negative will be withdrawn from therapy (beginning 6 months after the loss of HBsAg) and monitored carefully for evidence of return of HBV DNA activity or ALT elevations. Relapse will lead to reinstitution of therapy. The investigators believe that loss of HBsAg will occur in 5% to 10% of patients yearly, so that one-third of patients will be HBsAg negative by 5 years and two-thirds by 10 years. This study will thus indicate whether therapy of chronic hepatitis B should be based upon maintained suppression of HBV DNA to undetectable levels until loss of HBsAg, which may occur after years of therapy. This study may help define the factors that predict loss of HBsAg, or rather the duration of therapy necessary to achieve loss of HBsAg.

Patients with previous lamivudine ± adefovir resistance:

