- 1) Will combination therapy yield a higher response rate and prevent the development of further resistance than monotherapy in patients with previous antiviral resistance (lamivudine, adefovir and entecavir)? Response will be defined as HBV DNA  $<10^2$  IU/ml and normal ALT at 48 and 192 weeks. Samples of blood at yearly intervals that are HBV DNA positive will be tested for tenofovir (rtA194T) and emtricitabine (rtM204V/I and rtL180M) resistant mutations by direct sequencing. The investigators believe that the maintained virological and biochemical response will be higher in the combination arm compared to the monotherapy arm and the rate of further resistance will be lower at 48 and 192 weeks.

Patients who relapsed after withdrawal of lamivudine, adefovir or the combination of lamivudine plus adefovir:

- 1) We hypothesize that combination therapy will result in a greater proportion of subjects re-responding to re-institution of therapy. Response will be defined as an HBV DNA  $<10^2$  IU/ml and normal ALT at 48 and 192 weeks. For individuals who experienced HBeAg sero-reversion (HBeAg negative to positive) a response will also include loss of HBeAg or HBeAg seroconversion again. We further hypothesize that

combination therapy will prevent or delay the appearance of antiviral resistance compared to tenofovir monotherapy in persons who relapsed? To address this issue, the HBV polymerase gene will be sequenced from all serum samples at yearly intervals that are HBV DNA positive.

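### The plan names two different primary endpoints, and the section F version, read literally, counts patients taken off drug after HBsAg loss as week-192 non-responders

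*Combined protocol and SAP*

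**What the plan says.** Section F (Assessment of response) states: "The primary study endpoints will be a maintained full virological response after 48 weeks and 192 weeks of therapy". Its definitions describe a maintained response as a virological, serological, biochemical, histological or "combined response present at the time of last observation in a patient still receiving therapy". Response after stopping is a separate category, sustained, which requires at least six months off drug. HBsAg loss is called a complete response. Neither of these two is the primary endpoint.

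Hypotheses and Issues, treatment-naïve item 3, differs: "The primary response definition will be absence of detectable HBV DNA by PCR-based methods" (below 10^2 IU/ml) at weeks 48 and 192. It sets no condition on being on drug. Its secondary list includes response "at the time of last assessment (= maintained response", also without an on-therapy condition.

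Section I powers a pooled comparison in Groups A–D on full virological response, 94% against 70% at 4 years. It scores missing data and dropouts as failures.

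Sections D and F both require drug to be stopped after HBsAg loss confirmed over six months. Section F calls toxicity stops failures but does not say how clearance stops are scored.

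For patients with previous resistance and for relapsers, Hypotheses and Issues defines response as HBV DNA below 10^2 "IU/ml and normal ALT at 48 and 192 weeks". For relapsers with HBeAg sero-reversion, "a response will also include loss of HBeAg or HBeAg seroconversion again".

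**The concern.** The two statements of the primary endpoint score one group of patients differently. A patient who loses HBsAg, has it confirmed and is taken off drug as the protocol requires is no longer receiving therapy at week 192. Under item 3 that patient is a responder if HBV DNA is below 10^2 IU/ml. Under the section F wording the patient cannot be a maintained responder, despite having the outcome the plan ranks highest. A patient stopped less than six months before week 192 would not qualify as a sustained responder either.

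The week-192 result therefore depends on which definition the analyst adopts, and that choice could be made after results are seen. Under the literal wording, the comparison also loses power that the sample-size statement assumes it has.

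A side issue concerns the previously treated patients. Section I pools Groups C and D with the naïve patients and does not say that the normal-ALT condition stays out of the pooled test.

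**Working it through.** **Plan's own figure.** Inputs from section I: two-sided Fisher exact test, alpha 0.05, 94% against 70%, 50 per arm. Enumerating both binomials and rejecting when p ≤ 0.05 gives 85.7%, which matches the stated 86%.

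**Patients off drug by week 192.** Hypotheses and Issues (naïve item 4) forecasts HBsAg loss of 5–10% yearly and one-third of patients HBsAg-negative by 5 years. Assume a constant yearly rate r, six months' confirmation before stopping and no reinstatement. Time at risk is 192/52 − 0.5 = 3.19 years, and c = 1 − (1 − r)^3.19.

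- r = 5%: c = 15.1%.
- r = 10%: c = 28.6%. This rate implies 1 − 0.9^5 = 41% loss by 5 years, above the plan's one-third.
- Calibrated: r = 1 − (2/3)^(1/5) = 7.8%, so c = 22.8%.

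**Share of the trial affected.** The forecast stands under the naïve-patient questions. The Précis and the Protocol section give 40 naïve patients among 100, so s = 0.4c.

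**Power when these patients are scored as non-responders** (50 per arm; all who stop are assumed to have been responders otherwise). Two loss models are used:

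- Equal absolute loss: each rate becomes p − s.
- Proportional loss among responders: each rate becomes p(1 − s), assuming the same response rates in naïve and other patients.

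| Yearly loss | s | Equal absolute: rates, power | Proportional: rates, power |
|---|---|---|---|
| 5% | 6.0% | 88.0% vs 64.0%, 76.1% | 88.3% vs 65.8%, 71.5% |
| 7.8% (calibrated) | 9.1% | 84.9% vs 60.9%, 72.3% | 85.4% vs 63.6%, 64.7% |
| 10% | 11.4% | 82.6% vs 58.6%, 69.7% | 83.3% vs 62.0%, 60.0% |

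Under equal absolute loss the difference stays at 24 points, and power falls because both rates move toward 50%. Under proportional loss the difference becomes 24 × (1 − s), or 22.6 to 21.3 points over the 5–10% range.

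**Sensitivity.** Section D gives at least 60 patients in Groups A and B, which conflicts with its own caps of 20 + 20. With s = 0.6c and 5–10% yearly loss, power is about 49–72%. With the forecast applied to all patients (s = c), it is about 35–66%.

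**Week 48.** Time at risk is 48/52 − 0.5 = 0.42 years. This puts 1 − (1 − r)^0.42, about 2–4% of the patients covered by the forecast, off drug.

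**The case against.** The best defence is that section F's terms are descriptive categories and that nobody meant to penalise HBsAg clearance. No statement calls a clearance stop a failure. Section F labels toxicity stops as failures and does not do so for clearance, and its list of failure types omits clearance. Section I's missing-data rule does not catch these patients, because they remain in follow-up. The relapse definition speaks of events "after therapy is stopped in a patient who previously had a maintained full virological response", which credits the response held before stopping. All of this stands: the literal result is probably unintended. It still leaves two primary definitions and no rule for scoring these patients at week 192.

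Four stronger readings are tempting, and the documents do not support them.

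- **That power falls to 35%.** This applies a naïve-patient forecast to resistant and relapsed patients, and needs the 10% rate, which overshoots the plan's own 5-year figure, together with proportional loss.
- **That the rule removes more responders from the combination arm.** This follows only from the proportional model. Naïve item 1 expects similar HBV DNA decline in both arms.
- **That the ALT and HBeAg composites are rival primary endpoints.** The plan never calls them primary. The HBeAg condition concerns relapsers (Group E), who are outside the Groups A–D named in section I. Only the ALT condition in Groups C and D remains open.
- **That the plan declares clearance patients failures.** It does not say so. The result comes only from reading two section F statements together.

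**Conclusion.** The inconsistency is real and should be fixed. Section F and Hypotheses and Issues state different primary endpoints, and section I does not choose between them explicitly, although full virological response fits item 3.

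If the literal section F wording were applied, week-192 power would be about 60–76% instead of 85.7%, or about 65–72% when calibrated to one-third HBsAg loss by 5 years. The 35–66% range is an upper bound on the harm, not the main figure. The figures rest on 40 of 100 patients being naïve, 50 per arm, constant yearly loss, six months' confirmation, no reinstatement, and suppressed HBV DNA in everyone who stops. Power falls under both loss models; the between-arm difference shrinks only under proportional loss. If clearance patients are scored on their HBV DNA and remain below 10^2 IU/ml, the planned rates and power stand.

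**What to change.** State one primary endpoint in Hypotheses and Issues, section F and section I: HBV DNA below 10^2 IU/ml at the week-48 and week-192 visits. Score patients stopped under the HBsAg-clearance rule on their HBV DNA at that visit, and say that the value is obtained at week 192 in patients off drug.

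Give maintained response a single definition as the secondary last-assessment endpoint. Either drop the on-therapy condition or state that clearance stops are exempt; otherwise the same problem persists there.

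State that the ALT and HBeAg composites are secondary endpoints for previously treated patients. Toxicity stops, dropouts and missing data remain failures, as sections F and I already say.

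The off-drug follow-up intervals after the first six months differ between section E (3 to 12 months) and section F (every 12 weeks) and must be reconciled. The clinical stopping rule is unchanged.

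The cost is a short paragraph in sections F and I, matching edits to the hypotheses, and one HBV DNA value at week 192 for each patient off drug. Section F already has clearance patients on 4- or 12-week monitoring. Sample size and treatment do not change.
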